	 Sample size selected to allow detection of safety concerns in the
	broad PTSD population to be recruited for Stage 2
	 A maximum of 400 individuals will be screened in order to
	achieve the recruitment goal
	Stage 2
	• Total recruitment goal:
	\circ 120
	\circ 108 completers (90%)
	• Assignment ratio =1:1 for Active eTMS vs. Sham eTMS

Statistical Methods (Stage 1)	 Primary outcome time point = F1 Planned estimated effect size +0.8 SD_{difference}, for a difference in Active eTMS versus Sham eTMS group mean pre-post PCL-5 scores = 15, with pooled SD_{difference} = 18.68 Type 1 error = 0.05 (2-sided) Statistical power = 98.5 % Method of calculation – Sample size and power for given detectable difference between two mean difference scores using Student's t-test according to method of Dupont & Plummer Design variable is change in PCL-5 between BL and F1. Mean in a first responder population = 38.73 (SD = 18.68) (Morrison, Su, Keck, & Beidel, 2021) Clinically important difference (MCID) = 10 - 20 Adverse events characterized by: Frequency Relatedness Severity Type DSMB to review and make recommendations regarding: Whether to proceed to Stage 2 Protocol changes for Stage 2
Statistical Methods (Stage 2)	 Intention to Treat (ITT) population to analyze the primary outcome, with secondary analyses using Per Protocol (PP) population Primary outcome tested by linear regression of change score between Baseline (BL) and end of treatment (F1) at 5% Type 1 error rate Multiple linear regression imputation of missing data assuming missing at random (MAR), and best-case/worst-case sensitivity analyses Poolability of data from all sites tested Exploratory outcomes tested, as appropriate, according to level of data (e.g., categorical, ratio), number of time points at which measured, and fulfillment of statistical assumptions DSMB monitors emerging safety, efficacy, recruitment and performance data DSMB to recommend continuation/termination One interim analysis of efficacy data after approximately 50% completers Haybittle-Peto alpha-spending and stopping rule

STUDY SYNOPSIS	2
TABLE OF CONTENTS	. 10
LIST OF ABBREVIATIONS	. 13
INTRODUCTION AND RATIONALE	. 16
Post-Traumatic Stress Disorder	. 16
Treatment for Posttraumatic Stress (PTSD)	. 19
Repetitive Transcranial Magnetic Stimulation (rTMS)	. 20
Electroencephalogram (EEG) personalized Transcranial Magnetic Stimulation (eTMS)	. 25
Preliminary Data	. 26
STUDY OBJECTIVE	. 27
STUDY DESIGN	. 28
Stage 1	. 28
Stage 2	. 28

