A Certificate of Confidentiality (CoC) protects the privacy of research participants by prohibiting disclosure of identifiable, sensitive research information to anyone no connected to the research except when the participant consents or in a few other specific situations (potential harm to themselves or others). A CoC may be obtained through the National Institute of Health (NIH). Since this study comprises assessments of potential illicit opioid drug use, a CoC will be obtained before the study begins. All participants in the study will receive a CoC as part of their Informed Consent process. All trial personnel will be trained and tested to ensure they comply with the tenets of the CoC regarding every participant.

Withdrawal from Study

Participants have the right to withdraw from the study at any time, for any reason. The Investigator may withdraw a participant from the trial for the safety of the participant, other participants, or study personnel. The Investigator may similarly suspend or terminate only a participant's treatment protocol and may re-initiate a suspended treatment protocol. Participants who withdraw, or are withdrawn, from the study will be asked to complete Early Termination assessments. Participants for whom the treatment protocol only is suspended or terminated, are regarded as ongoing participants in the study, and will be asked to complete all data collection visits and data collection procedures regardless of treatment status.

The IRB may terminate the trial. The Food and Drug Administration may terminate the trial under an IDE. The study Sponsor may terminate the trial for the following reasons:

- Occurrence of unacceptable risk to the participants enrolled in the study
- Upon recommendation of the Data and Safety Monitoring Board to terminate the trial for futility or for safety reasons
- A business decision on the part of Sponsor to suspend or discontinue testing, evaluation, or development of the product

Participants who are withdrawn, or whose treatment protocols are suspended or terminated due to adverse events will be followed until resolution or stabilization of the adverse event, or until

30 days following the final study treatment received, whichever is sooner, unless it is not possible to do so.

Assignment of Participant Identification

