- 3. The F1 EEG may serve as the treatment-setting EEG for the Open Label period if treatment begins within 15 days of the collection of the F1 EEG. Otherwise, conduct another EEG within 15 days of the first Open Label treatment

Data to be collected

The data to be collected include, according to the schedule in the Schedules of Activities, above, include:

- DSM-5 PTSD Checklist (PCL-5)
- Veterans RAND 36-Item Health Survey(VR-36)
- TMS Screening Form (TMSs)
- Mini Mental Status Exam (MMSE)
- Columbia Suicide Severity Rating Scale (CSSRS)
- Ohio State University Traumatic Brain Injury Identification Method (OSU-TBI-ID)
- Drug History Questionnaire (DHQ)
- Life Events Checklist for DSM-5 (LEC-5)
- Clinical Global Impression (CGI)
- Computerized Neuropsychological Battery (Braincheck)
- Somatic Symptom, Anxiety, Depression Screen (PHQ-SADS)
- Alcohol Use Disorders ID Test (AUDIT)
- Morphine Equivalent Dose (MED)
- Opiate Craving Scale (OCS)
- Drug Abuse Screening Test (DAST-10)
- Pittsburgh Sleep Quality Index (PSQI) •
- Side Effects Questionnaire (SEQ)
- EEG/ECG •
- Brief Pain Inventory (BPI)
- Blinding Assessment
- Body Temperature
- Blood Pressure
- Concomitant treatments: background supportive, physical, and neuromodulatory
- Concomitant medications
- Concomitant illicit drug use
- Concomitant alcohol use
- Adverse Events
- Demographics/Military/First Responder
- Medical/Psychiatric History
- Pregnancy

PCL-5: The PCL-5 is a measure of severity of PTSD symptoms. . The PTSD Checklist-5 is a 20item self-report measure that assesses the 20 DSM-5 symptoms of PTSD. The PCL-5 has a variety of purposes including monitoring symptom change during and after treatment, screening individuals for PTSD, and making a provisional PTSD diagnosis. Each item ranges from 0 to 4 (0=not at all, 1=a little bit, 2=moderately, 3=quite a bit, 4=extremely), and a total score ranging from 0 to 80. It takes approximately 5 - 10 minutes to complete. It can be administered in 3 formats: without Criterion A (TE exposure), with a brief Criterion A assessment, or with the Life Events Checklist for DSM-5 (LEC-5) and extended Criterion A assessment. When used for provisional diagnosis, instead of for severity measurement, the DSM-5 diagnostic rubric is followed to assure distribution across the symptom clusters, but when other diagnostic measures Wave Neuroscience, Inc. Protocol eTMS-PTSD Rev 1.1 11 January 2024

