provide the diagnosis (i.e., the CAPS-5), a simple summation of severity scores across the 20 items may be used to determine probable PTSD. Initial research indicates that a cut off score of between 31 and 33 signals probable PTSD. (U.S. Department of Veterans Affairs, 2022) (Spoont, et al., 2013) A provisional PTSD diagnosis can be made by treating each item rated as 2 = "Moderately" or higher as a symptom endorsed, then following the DSM-5 diagnostic rule which requires at least: 1 B item (questions 1-5), 1 C item (questions 6-7), 2 D items (questions 8-14), 2 E items (questions 15-20). In order to avoid enrolling persons who do not have PTSD, criteria for the diagnostic rubric must be fulfilled AND a minimum PCL-5 score of 31 will be required. Evidence for the PCL for DSM-IV suggests that a 5-10 point change represents reliable change and a 10-20 point change represents clinically significant change. It is recommended to use 10 points of change as a minimum threshold for determining whether the improvement is clinically meaningful. Change score characteristics are currently being determined regarding reliable and clinically meaningful change. The VA recommends following the DSM-IV recommendations. The PCL-5 is the primary efficacy outcome for Stage 2 of this trial. Morrison et. al., in the first study on the PCL-5's psychometric properties for first responders in the United States, studied a sample of 133 first responders, including firefighters/EMT (76.7%) and police (23.3%). The mean total PCL-5 score was 38.73 (SD = 18.68, range 0-72). (Morrison, Su, Keck, & Beidel, 2021)

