
Stage 2

Stage 2 of the trial is intended to investigate efficacy and safety of the procedure in the target population. The primary efficacy outcome is a measure of PTSD symptom severity. PTSD symptom reduction will be calculated as the arithmetic reduction in PCL-5 scores between BL and F1. See the above Data Collection section for a description of this assessment.

Safety will be characterized by adverse event incidence, relatedness, severity, type, subsequent treatment/intervention required, and resolution status.

SAMPLE SIZE CONSIDERATIONS FOR STAGE 1

A convenience sample size of thirty (30) will be treated in the safety pilot stage in order to detect common adverse effects or safety concerns.

SAMPLE SIZE CONSIDERATIONS FOR STAGE 2

Sample size assumptions:

[figure not shown]
- Design variable is change in PCL-5 between BL and F1.
 - Mean in first responders = 38.73 (SD = 18.68) (Morrison, Su, Keck, & Beidel, 2021)
 - Primary outcome clinically important difference = 15(10-20) (U.S. Department of Veterans Affairs, 2022)
- Planned estimated effect size +0.8 SD_{difference}, for a difference in Active eTMS versus Sham eTMS group mean pre-post PCL-5 scores = 15, with pooled SD_{difference} = 18.68
- Assignment ratio =1:1 for Active eTMS vs. Sham eTMS
- 10% loss to followup

- Type 1 error = 0.05 (2-sided)
- Statistical power = .985
- Method of calculation Sample size and power for given detectable difference between two mean difference scores using Student's t-test according to method of Dupont & Plummer

Sample size requirements:

- Total completers: 108 (90% 54 per group) See Figure 2 below
- Total to be randomized:120 (60 per group)

FIGURE 2: Primary efficacy outcome, PCL-5. Statistical power by number of completers per treatment group for Type 1 error 0.05 (.985) and 0.01 (.938)

DATA AND SAFETY MONITORING BOARD

A Data and Safety Monitoring Board (DSMB) comprised of at least 3 **independent** subject matter, medical, clinical trial methods, and biostatistics experts will be constituted to review the protocol, recruitment progress, site performance, study conduct, and safety data. The Board will request analyses, and will make recommendations regarding study continuation, amendment, or termination, as well as the advisability of adding up to 3 additional research sites.

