The primary efficacy outcome analysis will be conducted on the ITT population. The primary efficacy outcome measure is arithmetic change in PCL-5 score between BL and F1. The primary efficacy hypothesis is the superiority of eTMS treatment over sham eTMS treatment in participants with PTSD. Missing values will be imputed. The analysis of the primary outcome will be a linear regression of the change in PCL-5 total score between BL and F1, with independent variables being the BL PCL-5 total score and a dummy variable for the two treatment groups.

Missing F1 PCL-5 total scores will be addressed using multiple imputation. Missing PCL-5 total scores will be estimated (i.e., imputed) from a linear regression model to be determined from observations in which the F1 PCL-5 score is not missing; covariates considered for inclusion in the model will be the BL PCL-5 total score, a dummy variable for treatment group, and other potentially associated variables (e.g., age, gender, PTSD severity, military status, and number of treatments. The linear regression model will be chosen using the LASSO method with cross-validation, implemented in SAS PROC GLMSELECT. The set of variables to be considered for inclusion will be determined before the imputation is performed. After the form of the linear regression model is determined, at least 20 data sets will be created with the missing F1 PCL-5 values imputed, using the linear regression analysis (linear regression of change in PCL-5 score on BL score and a dummy variable for treatment group)

will be performed for each of the imputation datasets. SAS PROC MIANALYZE will then be used to combine the regression results from the previous step and form the final MI analysis results. Since there will be multiple imputed values for each missing F1 PCL-5 score, the analysis will account for variability in the missing values. This process assumes that missing values are missing at random (MAR), i.e., they may depend on values of other variables measured at the same time, but not on the non-missing values. The following sensitivity analyses will be conducted for missing PCL-5 total scores at F1: 1) analysis of non-missing F1 PCL-5 total scores; 2) analysis in which missing F1 PCL-5 total scores will be replaced with the best PCL-5 total score possible; and 3) analysis in which missing F1 PCL-5 total scores will be replaced with the worst PCL-5 total score possible.

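### The best-case and worst-case missing-data analyses give both arms the same extreme score, so with similar dropout they nearly coincide and do not bound the treatment effect

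*Combined protocol and SAP*

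**What the plan says.** The section *Primary outcome efficacy analysis* (Statistical Analysis Plan for Stage 2) regresses the BL-to-F1 change in PCL-5 on baseline score and treatment in the ITT population. Missing F1 scores are multiply imputed under missing at random (MAR). Three sensitivity analyses follow. The first uses observed F1 scores only. The second is an "analysis in which missing F1 PCL-5 total scores will be replaced with the best PCL-5 total score possible". The third is an "analysis in which missing F1 PCL-5 total scores will be replaced with the worst PCL-5 total score possible". Neither replacement rule refers to treatment arm. The synopsis, under Statistical Methods (Stage 2), calls the pair "best-case/worst-case sensitivity analyses". No arm-specific, delta-adjusted or tipping-point analysis appears anywhere in the document.

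For the imputation model, the "covariates considered for inclusion in the model will be the BL PCL-5 total score, a dummy variable for treatment group", together with other variables such as age and gender, and LASSO with cross-validation then selects among them. Treatment and baseline are therefore candidates, not fixed terms.

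**The concern.** Readers take a best case and a worst case as the two ends of what the missing data could do to the result. This pair does not have that property. When the same value is put in for every dropout and the arms lose similar proportions, the value cancels from the between-arm comparison. Two nearly equal estimates would then be reported under labels that suggest they enclose the possible effects.

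The departure from MAR that threatens a positive finding is one that differs by arm: active dropouts worse than imputed, sham dropouts better. Neither replacement analysis examines it, and the observed-scores analysis does not either. Since the primary result rests on MAR, the trial would have no planned check on the assumption most open to challenge.

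A smaller, related point is that LASSO could drop the treatment term from the imputation model while the analysis model keeps it. Dropouts in both arms would then be imputed from a common prediction, which pulls the estimate toward zero.

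**Working it through.** **Inputs from the document**
- PCL-5 has "a total score ranging from 0 to 80" (*Data to be collected*), so best is 0 and worst is 80.
- Difference 15, SD 18.68, 54 completers and 60 randomised per arm, "10% loss to followup" (*Sample size considerations for Stage 2*). No split of the loss by arm is given.
- Final two-sided criterion 0.049 (*Data and Safety Monitoring Board*).
- A smaller effect to test, 10 points, from the PCL-5 description: "It is recommended to use 10 points of change as a minimum threshold for determining whether the improvement is clinically meaningful".

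**The plan's own figures.** A two-sample t-test with 54 per arm (106 df) gives power 0.9852 at alpha 0.05, against the stated .985, and 0.9371 at 0.01, against .938. Inflating for dropout, 108/0.90 = 120. The inputs reproduce.

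**General formula.** Let D be the completer difference, m the sham completer F1 mean, pA and pS the missing proportions in the active and sham arms, and c a common fill value. The benefit of active over sham is

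(1 − pS)m − (1 − pA)(m − D) + (pS − pA)c.

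The c = 0 result minus the c = 80 result is 80(pA − pS). If pA = pS = f, then c and m both drop out and each analysis gives (1 − f)D. Opposite extremes by arm give (1 − f)D − 80f and (1 − f)D + 80f.

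**Results**

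| Scenario | All missing = 0 | All missing = 80 | Opposite extremes by arm |
|---|---|---|---|
| D = 15, 10% missing per arm | 13.5 | 13.5 | 5.5 to 21.5 |
| D = 10, 10% missing per arm | 9.0 | 9.0 | 1.0 to 17.0 |
| D = 10, 5% missing per arm | 9.5 | 9.5 | 5.5 to 13.5 |
| D = 15, 9 active and 3 sham missing, m = 40 | 16.75 | 8.75 | 4.75 to 20.75 |
| D = 15, 3 active and 9 sham missing, m = 40 | 10.25 | 18.25 | 6.25 to 22.25 |

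For the 9/3 row: 0.95 × 40 − 0.85 × 25 = 16.75; adding (0.05 − 0.15) × 80 = −8 gives 8.75; the bounds are 16.75 − 0.15 × 80 = 4.75 and 16.75 + 0.05 × 80 = 20.75. For the 3/9 row: 0.85 × 40 − 0.95 × 25 = 10.25; adding 0.10 × 80 = 8 gives 18.25; the bounds are 10.25 − 0.05 × 80 = 6.25 and 10.25 + 0.15 × 80 = 22.25. In that row the best-score analysis gives the smaller effect, so the labels invert. The planned pair equals the bounds only if all missing data fall in one arm.

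The design sections give 140 randomised instead of 120. That does not matter here: 7 of 70 missing per arm gives the same first row.

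**Does baseline adjustment change this?** The planned regression was simulated with 6 of 60 missing per arm and a true difference of 15 (assumed baseline mean 50, SD 11, sham improvement 10, residual SD 18.68).
- Scores not clipped: 13.4 in both planned analyses, 5.4 to 21.4 for opposite extremes.
- Scores clipped to 0–80: the completer difference itself shrinks to 13.94. The planned analyses give 12.5 (SE 3.6, significant in 96% of trials) and 12.6 (SE 4.0, 93%). The unfavourable opposite-extremes analysis gives 4.6 (SE 4.0, 13%) and the favourable one 20.5 (100%).

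**Tipping point at 10% missing per arm.** SE = 18.68 × √(2/54) = 3.595. The critical t at two-sided 0.049 with 106 df is 1.9915, so significance needs a difference of 7.16. Shifting active dropouts δ points worse and sham dropouts δ points better than imputed lowers the estimate by 0.20δ; shifting only the active arm lowers it by 0.10δ.
- D = 10: (10 − 7.16)/0.20 = 14.2 points in opposite directions, or 28.4 in the active arm alone.
- D = 15: (15 − 7.16)/0.20 = 39.2 points, or 78.4 in the active arm alone.

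**The case against.** **Exact balance is uncommon.** If 12 of 120 are lost at random, a 6/6 split has a probability of only 24%. The expected gap between the two planned estimates is 3.4 points, and a gap of at least 5.3 (4/8 or more unequal) occurs 36% of the time. This stands: the pair carries some information when dropout is unequal. What it reflects, though, is the imbalance in dropout. The bounds with 12 missing always span 16 points, and the pair stays inside them unless one arm loses nobody.

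**The text does not say both arms.** True, but replacing all missing scores without mention of arm has one plain reading. If arm-specific extremes were intended, the same edit makes that clear.

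**The formula ignores baseline adjustment, and the two analyses are not redundant in precision.** In expectation, adjustment leaves the result intact, as the simulation shows. The standard errors do differ (3.6 against 4.0), so p-values will not be identical.

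**The planned effect is robust.** This stands. At 15 points, only implausibly large shifts remove significance. The fragility concerns a smaller observed effect.

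**Retention should limit missing data.** Those who withdraw "will be asked to complete Early Termination assessments", those who only stop treatment are followed at every data collection visit, and randomisation takes place just before the first treatment. The 5% scenario reflects this. The gap narrows but does not close.

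**The LASSO point is minor.** Agreed. In a small simulation with assumed covariates (150 trials per setting), treatment was dropped in 0% of trials at a difference of 15 and about 9% at 10. The bias is toward zero, by at most about the missing fraction.

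**Conclusion.** The concern holds. As written, the two extreme-value analyses do not bound the treatment effect, and with equal dropout their point estimates are the same. At the planned 10% loss, assumed equal between arms, they leave unseen a range of 8 points either side of the reported figure.

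The practical consequence depends on the observed effect. At 15 points the conclusion would survive any plausible departure from MAR. At 10 points, opposite shifts of about 14 points on the 80-point scale would remove significance, and nothing in the plan would show it.

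The figures rest on an assumed split of dropout by arm, on an assumed sham F1 mean of 40 for the unequal-dropout rows, and, for the tipping points, on an unadjusted comparison whose multiple-imputation standard error is about the completer value. The equal-dropout results do not depend on the F1 means. The primary analysis, sample size and alpha are unaffected. This should be corrected, but it does not undermine the design.

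**What to change.** In *Primary outcome efficacy analysis*:

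1. Make a delta-adjusted tipping-point analysis the main check for data missing not at random. Apply it to the multiple-imputation data sets already planned, with delta varied separately by arm, and report the combinations at which significance at 0.049 is lost.
2. Define the extreme analyses by arm: (a) missing active scores set to worst and missing sham scores to best; (b) the reverse. Present them as outer limits only, since 0 and 80 are implausibly extreme for a whole group of dropouts. Align the synopsis wording.
3. Force the treatment indicator and baseline PCL-5 into the imputation model, and let LASSO choose only among the auxiliary variables.

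The cost is SAP wording, a few lines of code and a little more analysis work. The stated worst case will look less favourable than under the present rule. The change should be made before unblinding, because a tipping-point analysis chosen afterwards would carry less weight.

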Poolability over study sites will be separately assessed. In a separate analysis the association between the primary endpoint and the study site will be explored. Both the main effect of study site and the interaction between study site and treatment group will be explored.

Additional Analyses of the Primary Outcome

Exploratory responder analyses will be conducted. To determine whether a greater percentage of Active-treated participants respond to study treatment than Sham-treated participants, the binomial z-test will be used to compare the Active-treated group to the Sham-treated group at a number of percentage reductions in PCL-5 scores as candidate values of a successful treatment response. A range of percentage reduction values will be investigated as possible discriminating values to assist in designing future trials regarding sample size justification and power analysis, should a trial in future be designed with a responder analysis as the primary outcome or a secondary outcome.

Other participant reported outcomes analyses

Other participant reported outcomes, including assessment of blinding, will be analyzed according to their level of data (e.g., quantitative, rank order, or categorical) and validity of statistical assumptions required (e.g., homoscedasticity and normality).

Electrophysiological data analyses

Quantitative EEG data collected at BL and F1 will be stored on hard disk and analyzed offline. Raw data of each record will be visually inspected to reject significant artifact contamination. Selective data will be further analyzed by fast Fourier transform (FFT) routine to yield four consecutive frequency bands – delta (0.5-4 Hz), theta (4-8 Hz), alpha (8-13 Hz) and beta (13-35 Hz). Power density of each frequency band of each channel will be used to measure the EEG changes after treatment. Statistical analysis will include data reduction by initial factor analysis. Difference between treatment groups at each recording time will be tested by repeated measures and regression of number of treatments by channel. It is anticipated that successful treatment will result in reductions in low frequency rhythms and increases in peak alpha frequency and correspondent narrow-band density. These changes in EEG variables will be further correlated with clinical and cognitive data to explore the hypothesis that EEG parameters could be a biomarker for PTSD.

STUDY SITE MONITORING

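### The exploratory EEG analysis defines no variable for the predicted rise in peak alpha frequency, and does not say how treatment arm is handled in the EEG-symptom correlation

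*Combined protocol and SAP*

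**What the plan says.** All of this is in the Stage 2 statistical analysis plan, under Electrophysiological data analyses.

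- **Bands:** the BL and F1 recordings are reduced by FFT to "delta (0.5-4 Hz), theta (4-8 Hz), alpha (8-13 Hz) and beta (13-35 Hz").
- **Measure of change:** "Power density of each frequency band of each channel will be used to measure the EEG changes after treatment".
- **Prediction:** successful treatment should lower slow-frequency activity and bring "increases in peak alpha frequency and correspondent narrow-band density".
- **Arm comparison:** "Difference between treatment groups at each recording time will be tested by repeated measures and regression of number of treatments by channel".
- **Link to symptoms:** "These changes in EEG variables will be further correlated with clinical and cognitive data", with the aim "to explore the hypothesis that EEG parameters could be a biomarker for PTSD".

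Three other places matter. The Equipment section has software find the dominant frequency between 8 and 13 Hz from the power spectra, in order to set treatment. Table 5 schedules an EEG at both BL and F1. The inclusion criteria require every participant to meet the PCL-5 diagnostic rubric and to score at least 31.

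**The concern.** There are two gaps and one matter of wording.

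First, part of the prediction concerns where the alpha peak lies and the power close to it, while the only stated measure is total power in fixed bands. Treatment here is tailored to each person's alpha frequency, so this prediction bears most directly on the device's rationale. With no defined variable, the channel, the peak-finding rule and the width of the narrow band could all be chosen after the data are seen.

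Second, if active treatment changes both EEG and PCL-5, the two changes correlate across the pooled sample simply because both differ by arm. Without an arm term, a treatment effect showing in two variables could be reported as an EEG-symptom relationship.

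Third, there is no group without PTSD, so the data cannot show that an EEG feature separates people with PTSD from people without it.

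**Working it through.** **The plan's own figure.** The EEG section gives no sample size, power or alpha. The only stated power is for PCL-5, in Sample Size Considerations for Stage 2: difference 15, SD 18.68, 54 completers per group, two-sided 0.05, power 0.985. The noncentral t (106 df) gives 0.9852, which reproduces it. The standardized effect is 15/18.68 = 0.80.

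**Does band power see a peak shift?** Take a synthetic Gaussian alpha peak with SD 0.5 Hz (an assumed shape). Its total area is 0.5 × √(2π) = 1.2533. Power by band:

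| Peak (Hz) | Delta | Theta | Alpha | Beta |
|---|---|---|---|---|
| 9.5 | 0.0000 | 0.0016 | 1.2517 | 0.0000 |
| 10.0 | 0.0000 | 0.0000 | 1.2533 | 0.0000 |
| 10.5 | 0.0000 | 0.0000 | 1.2533 | 0.0000 |
| 11.0 | 0.0000 | 0.0000 | 1.2533 | 0.0000 |

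Moving the peak from 10 to 11 Hz changes none of the four powers.

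**What does a pooled correlation show when there is no within-arm link?** Inputs:

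- PCL-5 arm effect d1 = 0.8 SD (from the plan)
- EEG arm effect d2 = 0, 0.3, 0.5 or 0.8 SD (assumed; the documents give no figure)
- within-arm correlation zero (assumed)
- 1:1 allocation
- n = 108, the PCL-5 completer count, taken as the number with EEG at both visits (assumed)

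With two equal arms, the pooled correlation is

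r = (d1·d2/4) / √[(1 + d1²/4)(1 + d2²/4)].

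For d2 = 0.5: (0.8 × 0.5/4) / √(1.16 × 1.0625) = 0.100/1.110 = 0.090.

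Fisher's z has mean atanh(r) × √(n − 3), here 0.0903 × √105 = 0.926. The two-sided rejection rate is Φ(0.926 − 1.96) + Φ(−0.926 − 1.96) = 0.152. The same steps for the other values, beside 20,000 simulated trials of 54 per arm:

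| EEG effect (SD) | Pooled r | Rejection, Fisher z | Rejection, simulated | Simulated, arm-adjusted |
|---|---|---|---|---|
| 0 | 0.000 | 5.0% | 5.0% | 5.1% |
| 0.3 | 0.055 | 8.7% | 8.9% | 5.1% |
| 0.5 | 0.090 | 15.2% | 15.6% | 5.1% |
| 0.8 | 0.138 | 29.6% | 30.4% | 5.1% |

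The Study Design section gives 126 completers instead of 108. I used 108 because the power statement rests on it. With n = 126, the Fisher-z rates for 0.3, 0.5 and 0.8 SD are 9.4%, 17.1% and 33.7%, so the choice does not change the conclusion.

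**The case against.** The strongest reply is that this is an exploratory analysis outside the listed Stage 2 outcomes, and that much of the concern comes from what the text leaves unsaid. Several stronger readings are tempting, and the documents do not support them.

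- **That the EEG analysis would miss what it predicts.** It would not miss all of it. Delta and theta power directly test the predicted fall in slow activity. A rise in narrow-band alpha power, other things equal, would also raise 8-13 Hz power. Only a shift of the peak within the band is invisible. The spectra are recorded at both visits, so what is missing is a definition, not data. The phrase about EEG changes follows directly after the mention of peak alpha frequency and may be meant to include it, but no method is given.
- **That the correlation is unadjusted for arm.** The plan does not say so; it states no model at all. By contrast, the primary analysis section names its treatment-group term explicitly, so silence here leaves a real choice open.
- **That the false-positive rate is known to be high.** The inflation depends on assumed EEG effects and disappears if treatment does not affect the EEG.
- **That the plan claims a diagnostic biomarker.** It only proposes to explore a hypothesis and does not say which kind of biomarker is meant. A sample made up entirely of people with PTSD can inform a severity or response marker.
- **That the regression on number of treatments is offered as dose-response, or that repeated measures is the wrong way to compare arms.** The plan makes no dose-response claim, and no fault in repeated measures has been shown.

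What remains after these concessions is the undefined peak-alpha and narrow-band variables, and the unspecified handling of arm.

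**Conclusion.** The concern holds in limited form. As written, the EEG measure does not register a peak shift within 8-13 Hz, and neither the predicted peak alpha frequency nor the individual narrow-band density has an analysed variable.

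The correlation step leaves the treatment of arm open. The plan itself expects treatment to move both EEG and PCL-5. Under that expectation, a pooled version would reject in about 9% to 30% of trials for EEG effects of 0.3 to 0.8 SD, when no within-arm relationship exists. With no EEG effect the rate is 5%, and adjusting for arm keeps it at about 5% throughout. These rates rest on the assumed EEG effects, zero within-arm correlation, the planned 0.8 SD PCL-5 effect and 108 participants with both recordings.

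Priority is minor, since nothing here touches the primary result.

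**What to change.** Amend the section on electrophysiological data analyses, keeping it exploratory:

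1. Add two analysed EEG variables, computed from the BL and F1 spectra: change in peak alpha frequency, and power in a narrow band around each participant's BL intrinsic alpha frequency. State the channels, the peak-detection rule, the band width and the frequency resolution.
2. Compute EEG-symptom associations adjusted for arm, and report them within each arm as well.
3. Because every participant has PTSD, describe any finding as a marker of symptom severity or of symptom change, not as a diagnostic biomarker.

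The band-power analysis and the repeated-measures comparison can stay as they are. The cost is some SAP wording and a little programming on recordings already planned, with no new visit, procedure or participant. The only thing given up is the breadth of the biomarker wording. The change should be made before the data are unblinded.
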